5.9 Required Follow-Up Visits and Assessments

[figure not shown]
Group 1 (Healthy Volunteers): Healthy volunteers will be seen in the Critical Limb Care Center once a week (every 7 days \pm 2 days) for a total of 4 weeks of follow-up. The following evaluations will be completed and data recorded in the REDCap eCRF:

- ♦ Photograph of the study device application site
- ♦ SAR Questionnaire (App. A)

Group 2 (Wound Care Subjects): After completion of treatment (completed when wound has healed or 3 months is reached), subjects will be seen by the principal or sub-investigator in the Critical Limb Care Center every 3 months \pm 14 days for 12 months to evaluate for any late-term issues of tolerance, side effects, and/or adverse reactions. The following evaluations will be completed and data recorded in the REDCap eCRF:

- ♦ Photograph of the study device application site
- ♦ Wound measurements
- ♦ Percent granulation tissue
- ♦ SAR Questionnaire (App. A)
- ♦ Concomitant medications

IRB# 1331496 Page 28 Version 6.0

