5.11 Subject Withdrawal or Discontinuation

Subjects have the right to withdraw from the study at any time and for any reason without penalty or loss of benefits to which the subject is otherwise entitled. If a subject decides to withdraw, all study assessments, tests, and procedures will be stopped. An exit interview will be requested to understand why the subject chose to withdraw. The subject will also be offered the option to have data collection from the electronic medical record to continue in order to track wound progression. The Investigators may withdraw the subject at any time to protect the health, safety, or welfare of the subject. At the last point of contact, the date and reason for discontinuation will be documented, and every effort should be made to follow-up the status of any ongoing adverse events prior to withdrawal.

[figure not shown]
Subjects that do not present for the initial Noxsano Bandage application appointment will be withdrawn from the study and replaced.

Study participation may continue per the Schedule of Events (section 5.1) until one of the following criteria applies:

Group 1:

♦ Unacceptable adverse reactions warranting discontinuation of treatment in the opinion of the Investigators: Subjects experiencing any allergic reaction or infection at the device application site will be removed from study treatment.

IRB# 1331496 Page 29 Version 6.0

Group 2:

- ♦ Unacceptable adverse reactions warranting discontinuation of treatment in the opinion of the Investigators: Subjects experiencing any allergic reaction or infection at the device application site will be removed from study treatment.
- ♦ *Missed weekly treatment visits and discontinuation from study treatment*: Weekly treatment visits will be indicated as "missed" if the deviation from the planned date is > 2 days (i.e., 3 or 7 days ± 2 days, during the 3 month study period). If a subject misses 2 consecutive treatment visits, they will be removed from study and not replaced.

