- ♦ *Missed study follow-up visits:* Subjects who miss two consecutive follow-up visits will be contacted as described in section 5.12 in order to determine whether they wish to withdraw for the study or re-establish regular study follow-up visits. If subjects are able to re-establish study follow-up visits they may remain on the study. If the subject is unable to be contacted through the procedures outlined in section 5.12 data collection from the electronic medical record may continue, but the subject will be considered "lost to follow-up".
- ♦ Wound healing and discontinuation from study treatment: Clinical benefit may be determined during the treatment process by documentation of a healed ulceration, at which time the study device application will be discontinued. The post-treatment follow-up period will then begin for observation of late side effects and/or adverse reactions.
- ♦ *No evidence of wound healing at 2 months.* If a subject has no evidence of decreased wound surface area at 2 months (8 week treatment visit), the patient will be returned to standard and established techniques consistent with the wound etiology, and study follow-up will be discontinued.
- ♦ Wound < 50% healed at the completion of the study treatment period and discontinuation from study follow-up: If after 3 consecutive months (12 weeks) of treatment with the study device the wound does not exhibit at least a 50% decrease in surface area (cm²), the subject will be returned to standard and established techniques consistent with the wound etiology, and study follow-up will be discontinued. Clinical benefit experienced after the three-month treatment period, but not during the treatment period is not anticipated

In the absence of discontinuation due to adverse reactions (for both Groups 1 and 2) or wound healing outcomes (for Group 2 only) as indicated above, treatment may continue per the Schedule of Events (section 5.1) until one of the following criteria applies:

- ♦ Subject decision to withdraw from treatment (partial consent) or from the study (full consent),
- ♦ Death, or
- ♦ Funder reserves the right to temporarily suspend or prematurely discontinue this study.

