5.13 Compensation

Participant compensation will be done using a method approved by OhioHealth Research Institute (OHRI) Research Business Services. OhioHealth Associates enrolled in the healthy cohort will not be compensated.

Group 1: Compensation for healthy volunteers will be disbursed for the Baseline visit, the completion of the treatment period on Day 3, and the weekly 4 week follow-up period resulting in up to \$150 in total compensation (see compensation milestones below).

Time Point	Compensation Amount
Baseline	\$25
Completion of treatment	\$25
Week 1 follow-up	\$25
Week 2 follow-up	\$25
Week 3 follow-up	\$25
Week 4 follow-up	\$25

[figure not shown]
Subjects who discontinue study participation in Group 1 or Group 2 due to unacceptable adverse reactions per section 7.0 will receive a one-time discontinuation payment of \$25. Those subjects that discontinue, withdraw, or are lost to follow-up will not receive any further compensation.

Group 2: Compensation for wound care subjects will be disbursed for the completion of the treatment period (completed when wound has healed, subject is transitioned to standard of care techniques, or 3 months is reached, whichever comes first), and disbursed for each completed follow-up visit during the 12 month follow-up period resulting in up to \$125 in total compensation (see compensation milestones below).

Time Point	Compensation Amount		
Completion of treatment	\$25		
3-month follow-up	\$25		
6-month follow-up	\$25		
9-month follow-up	\$25		
12-month follow-up	\$25		

Subjects who discontinue study participation due to unacceptable adverse reactions per section 7.0 will receive a one-time discontinuation payment of \$25. Those subjects that discontinue, withdraw, or are lost to follow-up will not receive any further compensation

IRB# 1331496 Page 31 Version 6.0

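### Section 5.11 ends study follow-up, not only device treatment, for Group 2 non-responders, so among subjects reaching the 8- and 12-week assessments only responders have the late-safety visits

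*Combined protocol and SAP*

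**What the plan says.** The Protocol Summary and sections 3.3, 5.1 and 5.9 describe three-monthly visits over the year after Group 2 treatment, and all give late safety as their purpose. None makes attendance depend on wound response. Section 5.9 applies them as follows: "After completion of treatment (completed when wound has healed or 3 months is reached), subjects will be seen by the principal or sub-investigator".

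Section 5.11 then sets Group 2 rules by wound outcome:

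- **Healed.** The device is stopped and observation starts: "The post-treatment follow-up period will then begin for observation of late side effects and/or adverse reactions".
- **No decrease in area at the 8-week visit.** "the patient will be returned to standard and established techniques consistent with the wound etiology, and study follow-up will be discontinued". No reason is given.
- **Less than a 50% decrease after 12 weeks.** The consequence is the same. The only reason given is: "Clinical benefit experienced after the three-month treatment period, but not during the treatment period is not anticipated".

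A clause earlier in section 5.11 makes the schedule subject to these rules: "Study participation may continue per the Schedule of Events (section 5.1) until one of the following criteria applies". The section also asks staff to follow up adverse events that are still open before a subject leaves. Section 7.3 requires every adverse event that is observed or reported after consent to be recorded.

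**The concern.** This is the first clinical study of the device, with 10 wound subjects, and the year of follow-up exists to look for late harm. Section 5.11 decides who receives it by efficacy response. The reason attached to the 12-week rule concerns later benefit, which says nothing about later harm.

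If late risk is unrelated to response, the cost is precision only. If it is related, the description of late safety is skewed, and the study could not show this because the comparison group is not observed.

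**Working it through.** **Step 1: trace each Group 2 path in section 5.11, for subjects who reach the assessments.**

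| Wound outcome | Visits at 3, 6, 9 and 12 months |
|---|---|
| Healed by 12 weeks | Held |
| Not healed, at least 50% decrease at 12 weeks | Held (no stopping rule applies; section 5.9 governs) |
| Some decrease at 8 weeks, under 50% at 12 weeks | Stopped |
| No decrease at 8 weeks | Stopped |

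Two other groups lie outside this claim. Subjects with an unacceptable reaction are removed from treatment, with follow-up not specified. Subjects who miss two consecutive treatment visits are removed from the study.

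**Step 2: look for anything that restores observation.**

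- The provision on open adverse events covers events that have already begun.
- Section 7.3 sets no end date for recording, but depends on someone observing or reporting the event.
- Section 5.10 collects unscheduled-visit data during study participation, which has ended for these subjects.
- Medical-record collection is mentioned for subjects who withdraw ("offered the option to have data collection from the electronic medical record to continue in order to track wound progression") and for those lost to follow-up ("data collection from the electronic medical record may continue"), but not for those stopped under the two response rules.

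No scheduled contact would therefore detect a new late event in a non-responder.

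**Step 3: size.** The plan has no figure to reproduce: it gives no derivation for the 10 subjects, no non-response rate and no late-event rate. The following is an illustration.

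Inputs: n = 10 (section 3.2). Assumption: 30–50% non-response and no other loss. Followed: 10 × (1 − 0.3) = 7, or 10 × (1 − 0.5) = 5.

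With zero late events, the two-sided exact (Clopper-Pearson) 95% upper limit is 1 − 0.025^(1/n). The chance of seeing at least one late event at true risk p is 1 − (1 − p)^n.

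| Followed | Upper limit, 0 events | At least one event, p = 10% | At least one event, p = 20% |
|---|---|---|---|
| 10 | 30.8% | 65.1% | 89.3% |
| 7 | 41.0% | 52.2% | 79.0% |
| 5 | 52.2% | 41.0% | 67.2% |

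**Step 4: direction of bias.** Suppose half respond.

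- Late risk 10% in responders and 30% in non-responders: the risk in all treated is 0.5 × 10% + 0.5 × 30% = 20%, and the risk in those observed is 10%.
- The two risks exchanged: 20% in all treated and 30% in those observed.
- Equal risks: no bias.

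These risks are assumptions, and the documents do not favour any of the three cases.

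**The case against.** The best defence is that section 5.11 is a specific exception, written on purpose. This largely stands. A reader might infer that 5.11 contradicts 3.3, 5.1 and 5.9. However, 5.11 expressly limits the schedule, and the title of its 12-week rule names both completion of treatment and the end of follow-up, which is the case section 5.9 describes.

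Other stronger readings are tempting, and the documents do not support them:

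- **Section 5.13 as a conflict.** It treats treatment as "completed when wound has healed, subject is transitioned to standard of care techniques, or 3 months is reached, whichever comes first", but this defines a payment milestone. Follow-up is paid per visit completed, which is compatible with 5.11.
- **Non-responders are watched less than subjects who leave.** For subjects who withdraw, assessments stop and record collection is optional and aimed at wound progression. The lost-to-follow-up provision concerns people who had already entered follow-up.
- **Symptom resolution goes unseen.** Section 7.1.1 expects symptoms to resolve 7–10 days after removal, possibly 30 days or more, and Group 1 has four weekly visits after removal. But Group 2 responders also have no scheduled visit until 3 months ± 14 days. That gap is common to both, and keeping the later visits would not close it.
- **Late safety will look too favourable.** Step 4 shows that the direction is unknown.

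It also stands that open adverse events must be followed up, and that Group 2 comes from the treating centre's own patients (section 3.2), so some late events may surface in routine care. Section 9.0 defines no late-event rate. Without a control group, late events are hard to attribute in any subject. Even full follow-up leaves an upper bound of 31%.

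**Conclusion.** The concern holds as a design weakness of minor to moderate weight. Followed exactly, section 5.11 selects the late-safety sample on efficacy response, and the one reason it offers does not bear on harm.

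Under the assumed 30–50% non-response with no other loss, 5–7 of 10 subjects are followed and the zero-event bound rises from 31% to 41–52%. The selection itself follows from the text and needs none of these figures. On-treatment safety and the primary and secondary efficacy endpoints are unaffected.

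Confidence is high for the wording of section 5.11. It is lower for the absence of any other post-treatment observation, because section 10.0 and the Group 2 consent form were not available.

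A separate inconsistency sits nearby. Section 9.0 returns subjects to standard care at 2 months if improvement is below 50%, whereas sections 2.2, 3.3 and 5.11 do so if there is no decrease. Section 9.0 does not mention follow-up, so this does not change the point above. The passages must be reconciled, and this review does not choose between them.

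**What to change.** In section 5.11, separate the end of device treatment from the end of safety observation, and leave the return to standard care as written.

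- Keep the 3-, 6-, 9- and 12-month assessments for subjects stopped under the 8-week and 12-week rules.
- For those who will not attend, offer, with consent, the medical-record collection already allowed for withdrawn and lost subjects, extended to adverse events.
- Report late safety with the number of treated subjects not observed and the reason for each.
- Failing that, limit late-safety conclusions to the subjects followed.
- Separately, reconcile the 2-month criterion in section 9.0 with sections 2.2, 3.3 and 5.11.

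Cost: up to four visits and 4 × $25 = $100 in stipends per affected subject. For 3–5 subjects this is 12–20 visits and $300–500, plus staff time and a protocol and consent amendment. It stays within the 15 months and $125 per subject already stated for Group 2.

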5.12 Lost to Follow-Up

The subject may be lost to follow-up after 3 documented phone calls and a certified letter has been mailed to the subject in order to obtain compliance with study requirements. These subjects will not be replaced.

IRB# 1331496 Page 30 Version 6.0

5.13 Compensation

Participant compensation will be done using a method approved by OhioHealth Research Institute (OHRI) Research Business Services. OhioHealth Associates enrolled in the healthy cohort will not be compensated.

Group 1: Compensation for healthy volunteers will be disbursed for the Baseline visit, the completion of the treatment period on Day 3, and the weekly 4 week follow-up period resulting in up to \$150 in total compensation (see compensation milestones below).

Time Point	Compensation Amount
Baseline	\$25
Completion of treatment	\$25
Week 1 follow-up	\$25
Week 2 follow-up	\$25
Week 3 follow-up	\$25
Week 4 follow-up	\$25

[figure not shown]
Subjects who discontinue study participation in Group 1 or Group 2 due to unacceptable adverse reactions per section 7.0 will receive a one-time discontinuation payment of \$25. Those subjects that discontinue, withdraw, or are lost to follow-up will not receive any further compensation.

Group 2: Compensation for wound care subjects will be disbursed for the completion of the treatment period (completed when wound has healed, subject is transitioned to standard of care techniques, or 3 months is reached, whichever comes first), and disbursed for each completed follow-up visit during the 12 month follow-up period resulting in up to \$125 in total compensation (see compensation milestones below).

Time Point	Compensation Amount		
Completion of treatment	\$25		
3-month follow-up	\$25		
6-month follow-up	\$25		
9-month follow-up	\$25		
12-month follow-up	\$25		

Subjects who discontinue study participation due to unacceptable adverse reactions per section 7.0 will receive a one-time discontinuation payment of \$25. Those subjects that discontinue, withdraw, or are lost to follow-up will not receive any further compensation

IRB# 1331496 Page 31 Version 6.0

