2.0 STUDY OBJECTIVES AND ENDPOINTS

2.1 Primary Objective

Group 1 (Safety): Healthy Volunteers. The initial phase of the study is designed to determine the safety of the study device in healthy volunteers without wounds. If there are no issues with tolerance, side effects, or adverse reactions in healthy volunteers, the second phase of the study will proceed with active wound care subjects.

For the purposes of this study, if two subjects experience an unacceptable adverse reaction warranting discontinuation of treatment in the opinion of the Investigators during the initial phase of the study, the study will be halted and the second phase (and the remainder of the initial phase, if applicable) will not be completed. Allergic reactions and infections at the bandage site will be considered unacceptable at any clinical severity; other adverse reactions will be deemed "unacceptable" by the Investigators on a case-by-case basis dependent upon clinical severity (App. A).

Group 2 (Efficacy): Wound Care Subjects. The second phase of the study is designed to determine the effectiveness of the study device in wound healing in subjects with active wounds (see Primary & Secondary Endpoints below).

[figure not shown]

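### The payment rules in section 5.13 can cost a subject up to $100 when an adverse reaction ends participation, and sections 5.11 and 5.13 leave open when that happens

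*Combined protocol and SAP*

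**What the plan says.** **Payments (5.13).** Group 1 receives $25 at Baseline, $25 for completing treatment on Day 3, and $25 at each of four weekly follow-up visits. Group 2 receives $25 on completing treatment and $25 at each of the 3-, 6-, 9- and 12-month visits. For Group 2, moving to standard-of-care techniques counts as completing treatment. OhioHealth associates in Group 1 are unpaid.

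**Early exit (5.13).** The trigger is leaving the study: "Subjects who discontinue study participation in Group 1 or Group 2 due to unacceptable adverse reactions per section 7.0" get one $25 payment. The section then says: "Those subjects that discontinue, withdraw, or are lost to follow-up will not receive any further compensation".

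**Removal (5.11).** For both groups: "Subjects experiencing any allergic reaction or infection at the device application site will be removed from study treatment". The lead-in to the list lets study participation run until a listed criterion applies, but the criterion itself speaks only of treatment. The two non-healing criteria in the same list state outright that follow-up stops. The adverse-reaction criterion does not.

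**Halt rule (2.1, repeated in 3.3 and 5.7).** Two unacceptable reactions in the initial phase, as judged by the investigators, halt the study. "Allergic reactions and infections at the bandage site will be considered unacceptable at any clinical severity"; other reactions are judged case by case on severity.

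**The concern.** Group 1 is a 10-person safety phase without a control group, and its result decides whether Group 2 opens. Section 1.3.5 says healthy volunteers were included because the porcine work could not show irritation. What volunteers disclose, and when, is therefore central to the phase.

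An allergic reaction or infection at the site leads to removal whatever its severity. If removal ends participation, a volunteer who discloses one early gives up most of the remaining payments, while one who waits does not. Section 7.1.1 expects symptoms 24 to 72 hours after application. No visit is scheduled between Day 0 and Day 3, so early detection in that window depends on the volunteer calling in. The halt threshold is only two subjects, so one undisclosed reaction could change the decision. In Group 2 no halt rule is at stake, but the reaction count could be affected in the same direction.

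If visits stop along with payment, the study also loses sight of how these reactions resolve. Section 7.1.1 expects resolution 7 to 10 days after removal, and possibly 30 days or more.

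**Working it through.** **1. The plan's own totals.**
- Group 1: 6 × $25 = $150, as stated.
- Group 2: 5 × $25 = $125, as stated.

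**2. Net loss if removal ends participation.** Net loss = full total − payments already earned − $25 discontinuation payment.

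| Point of leaving | Earned | Net loss |
|---|---|---|
| Group 1, after Baseline, before Day 3 payment | $25 | 150 − 25 − 25 = $100 (67% of 150) |
| Group 1, after Day 3 payment | $50 | 150 − 50 − 25 = $75 |
| Group 1, after Week 1 / 2 / 3 visit | $75 / $100 / $125 | $50 / $25 / $0 |
| Group 2, on treatment, completion payment not earned | $0 | 125 − 0 − 25 = $100 (80% of 125) |
| Group 2, on treatment, return to standard care earns completion payment | $25 | 125 − 25 − 25 = $75 (60% of 125) |

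The Group 1 rows after Day 3 have little practical force. The device comes off on Day 3, so no treatment remains to be stopped, and no passage says a reaction seen later ends the visits.

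**3. Net loss if the subject stays in paid follow-up.** Only the completion payment can be missed, so the loss is at most $25. It is $25 − $25 = $0 if the discontinuation payment is also made.

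**4. Which reading applies.** The 5.11 lead-in and the wording of 5.13 point to the end of participation. The 5.11 criterion itself (treatment only), and its contrast with the non-healing criteria, point to continued follow-up. The text does not settle it.

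**5. Illustration for the halt rule (Group 1 only).** Let p be the true probability of an unacceptable reaction and r the share disclosed. Both are assumptions; the documents give neither. With q = p × r, P(at least 2 of 10) = 1 − (1 − q)^10 − 10q(1 − q)^9.

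| p | r = 100% | r = 75% | r = 50% |
|---|---|---|---|
| 0.10 | 0.264 | 0.170 | 0.086 |
| 0.20 | 0.624 | 0.456 | 0.264 |
| 0.30 | 0.851 | 0.695 | 0.456 |

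The table shows how sensitive a two-subject rule is to missed reactions. It applies r to all ten volunteers and to every reaction, including visible ones and those in unpaid associates, so it is not an estimate of the effect of the payment rule.

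**The case against.** The best defence is that the payment rule penalises leaving, not speaking. A reported reaction that does not end participation costs nothing. Itch and pain, which depend most on what the subject says, are tolerance items in 7.1.1 and carry no automatic removal; itching is even expected in most Group 2 subjects. This stands. It does not cover allergic reactions and infections at the site, for which removal is automatic.

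A second defence is that 5.11 removes such subjects only from treatment, so paid follow-up may continue and the loss may be $25 or nothing. This also stands as a possible reading. However, 5.13 does not say so, and a subject reading that section could reasonably expect to forfeit the rest.

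A third is that detection does not rest on self-report alone. A reader might infer that a reaction between Day 0 and Day 3 becomes known only if the volunteer calls. The documents do not support that. On Day 3 the volunteer attends, the device is removed, the site is photographed and the SAR questionnaire is completed (5.1, 5.7, 5.8). Given the resolution times in 7.1.1, a visible reaction would usually still be present. What remains is early detection before Day 3, and symptoms that leave no visible sign or fade by then.

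**Conclusion.** The point holds as a plausible, unquantified disincentive to early disclosure, together with an unresolved inconsistency between 5.11 and 5.13. If removal ends participation, the net loss is up to $100 in Group 1 before the Day 3 payment, and $75 to $100 in Group 2 during treatment. If the subject stays in paid follow-up, it is at most $25 before any offset. Unpaid associates lose nothing.

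Three stronger readings are tempting and should not be adopted:
- That the rules are shown to bias the reaction count. The effect on behaviour is an inference from incentives; nothing in the documents measures it.
- That the chance of halting falls by a stated amount. Those figures rest entirely on assumed reaction and disclosure rates.
- That the Group 2 loss weakens the halt rule. That rule covers the initial phase only.

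The change is still worth making. The forfeiture is a stated rule, it falls on the subjects whose reactions the safety phase exists to observe, and it is cheap to remove.

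**What to change.** In 5.13, replace the separate $25 discontinuation payment and the forfeiture, for these subjects, with wording such as: *Subjects whose device is stopped early for an adverse reaction receive the completion-of-treatment payment and the usual $25 for each scheduled safety visit they attend, on the same terms as other subjects.* Keep the rule that visits not attended are not paid.

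Reconcile 5.11 with 5.13 so that both say whether a subject removed from treatment for a reaction stays in scheduled follow-up. The payment sentence works only if those visits exist. If participation ended at removal, a Group 1 volunteer removed before Day 3 would receive $25 + $25 = $50 and still be $100 short of $150.

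Cost: at most $100 more per affected subject (150 − 50 in Group 1; 125 − 25 in Group 2), so at most 20 × $100 = $2,000 if every subject were affected, plus protocol and consent wording. The visits are already in the schedule of events, so no new assessments are added. If the reconciled text keeps these subjects in follow-up, up to four planned visits each would be held that might otherwise have lapsed.
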